### ***Slit-lamp examination***

Descriptive statistics of slit-lamp examination will be provided separately at baseline and at the time of first abnormal slit lamp after occurrence of a treatment-emergent corneal event, and at the time of the worst BCVA value during a treatment-emergent corneal event for participants experiencing treatment-emergent corneal events (CMQ). The outcome (normal, abnormal), and for abnormal findings, the type of lesions and the distribution, will be described by laterality (unilateral, bilateral, all).

## **4.8 OTHER ANALYSES**

### **4.8.1 PK analyses**

PK analyses will be performed on the PK population as defined in [Section 3](#).

#### **4.8.1.1 *Tusamitamab ravtansine***

##### **4.8.1.1.1 *Noncompartmental analysis at Cycle 1 and Cycle 4 in Part 1 (safety run-in)***

The PK parameters will be calculated using non-compartmental methods from tusamitamab ravtansine concentrations will include, but may not be limited to, those listed in [Table 11](#).

**Table 11 - List of PK parameters and definitions**

Parameters	Cycle 1	Cycle 4	Definition
$C_{eo1}$	✓	✓	Concentration observed at the end of IV infusion
$C_{max}$	✓	✓	Maximum concentration observed after infusion
$t_{max}$	✓	✓	Time to reach $C_{max}$
$C_{last}$	✓	✓	Last concentration observed above the lower limit of quantitation after infusion
$t_{last}$	✓	✓	Time of $C_{last}$
$AUC_{last}$	✓	✓	Area under the plasma concentration versus time curve calculated using the trapezoidal method from time zero to $t_{last}$
$AUC_{tau}$	✓	✓	Area under the plasma concentration versus time curve calculated using the trapezoidal method from time 0 to 14 days

Parameters	Cycle 1	Cycle 4	Definition
AUC	✓		AUC from time zero extrapolated to infinity according to the following equation: $AUC = AUC_{last} + (C_{last}/\lambda_z)$ Extrapolation should not exceed more than 30% of total AUC. If $AUC_{ex} > 30\%$ , the value will be reported and not taken into account in descriptive statistics and derived parameters will not be calculated.
CL	✓		Total body clearance of a drug from plasma calculated using the following equation from AUC, after single dose: $CL = Dose/AUC$
CL ss	✓		Total body clearance of the drug from the plasma after IV administration calculated after repeated dosing, using the following equation: $CL_{ss} = Dose/AUC_0 - \tau$ , $\tau$ being the dosing time interval (14 days)
V ss	✓		Volume of distribution in the terminal phase calculated according to the following equation: $V_{ss} = CL \times MRT$ with $MRT = AUMC/AUC(-T_{inf}/2$ if infusion) MRT being the Mean Residence Time of a molecule in the body; AUMC is the area under the curve of the moments and $T_{inf}$ is the duration of infusion.
t 1/2z	✓	✓	Terminal half-life associated with the terminal slope determined according to the following equation: $t_{1/2z} = 0.693/\lambda_z$ Where $\lambda_z$ is the slope of the regression line of the terminal phase of the plasma concentration versus time curve, in semi-logarithmic scale. Half-life is calculated by taking the regression of at least 3 points on the terminal slope.

Individual concentrations and PK parameters will be listed and summarized by dose level (if applicable) using descriptive statistics (such as the number of observations, arithmetic and geometric means, median, standard deviation, standard error (SE), coefficient of variation (CV), minimum, and maximum).

In addition, individual and mean concentration profiles over time will be plotted by dose level (if applicable).

These descriptive statistics will be provided by PKDM department at Sanofi.

#### 4.8.1.1.2 Population PK analysis

The population PK analyses will be described in a specific document and the results will be presented separately from the clinical study report.

#### 4.8.1.1.3 Ctrough over cycles

Ctrough is defined as a sample collected before dosing. All concentration values below the LLOQ will be treated as zero in individual listing and respective descriptive statistics. Geometric mean will not be computed in case at least one concentration is below LLOQ.

Individual observed predose concentrations ( $C_{trough}$ ) and concentrations observed at end of infusion ( $C_{eo1}$ ,  $C_{eo1+1h}$  if any) will be tabulated and summarized with standard descriptive statistics by dose level (if applicable) and by visit.

For the descriptive statistics,  $C_{trough}$  following any dose reduction or preceding dose delay as defined in [Section 4.7.1.2](#) will be excluded.  $C_{eo1}$  and  $C_{eo1+1h}$  will be excluded following dose reduction.

A graphical representation of mean  $C_{trough}$  ( $\pm SD$ ) profile over time, by dose level (if applicable), will be provided throughout the course of treatment.

#### **4.8.1.2 *Immunogenicity impact on PK***

The impact of immunogenicity on PK will be assessed graphically by plotting individual  $C_{trough}$  profiles of participants with treatment-emergent ATA along with mean ( $\pm SD$ )  $C_{trough}$  profile of participants without treatment-emergent ATA over cycles. In addition, for participants with treatment-emergent ATA, each ATA positive, negative and inconclusive sample status will be flagged. A boxplot for participants without treatment-emergent ATA will also be displayed at each timepoint along with individual concentrations for participants with treatment-emergent ATA. A flag for ATA positive, negative and inconclusive sample status will also be used.

Descriptive statistics of  $C_{trough}$  for participants without treatment-emergent ATA will be provided by cycle.

#### **4.8.1.3 *Ramucirumab***

All concentration values below the LLOQ will be treated as zero in individual listing and respective descriptive statistics. Geometric mean will not be computed in case at least one concentration is below LLOQ.

Individual observed predose concentrations ( $C_{trough}$ ) and concentrations observed at end of infusion ( $C_{eo1}$ ) will be tabulated and summarized with standard descriptive statistics by dose level (if applicable) and by visit.

For the descriptive statistics,  $C_{trough}$  following any dose modification (delay or reduction as defined in [Section 4.7.1.2](#)) will be excluded.  $C_{eo1}$  will be excluded following dose reduction.

A graphical representation of mean  $C_{trough}$  ( $\pm SD$ ) profile over time will be provided throughout the course of treatment.

#### **4.8.1.4 *IgG***

In the all-treated population, the level of IgG in blood at pre-infusion of Cycle 1 Day 1 will be summarized with standard descriptive statistics (such as the number of observations, arithmetic and geometric means, median, standard deviation, coefficient of variation, minimum and maximum) for tusamitamab raptansine. A listing will also be provided.

#### 4.8.2 Immunogenicity analyses

Participant's ATA status, response variable, and kinetics of ATA responses (see definitions below) will be summarized on the ATA population.

Kinetics of ATA responses will be described for participants with treatment-induced ATA and for participants with treatment-boosted ATA, separately. Time to ATA onset and duration of ATA will be described with minimum, Q1, median, Q3, and maximum statistics.

Peak titer will be described with minimum, Q1, median, Q3, and maximum statistics for participants with treatment-induced ATA and for participants with treatment-boosted ATA, separately.

Sample status (negative, positive, inconclusive) and titers will also be described overtime using descriptive statistics.

The impact of positive immune response on efficacy, PK, and safety variables may be further explored, depending on ATA incidence.

##### *Participant's ATA status*

- Participants with **pre-existing ATAs** correspond to participants with ATAs present in samples drawn before first administration of intervention. Participants with missing ATA sample at baseline will be considered as without pre-existing ATA.
- Participants with **treatment-emergent ATA** correspond to participants with at least 1 treatment-induced/boosted ATA.
  - Participants with **treatment-induced ATAs** correspond to participants with ATAs that developed at any time after first IMP administration and without pre-existing ATA (including participants without pre-treatment samples).
  - Participants with **treatment-boosted ATAs** correspond to participants with pre-existing ATAs that are boosted at any time after first IMP administration to a significant higher titer than the baseline. A 2-fold serial dilution schema is used during titration, so at least a 4-fold increase will be considered as significant.
- Participants with **unclassified ATA** correspond to participants with pre-existing ATAs that cannot be classified as treatment-boosted ATA because of missing titer(s) (ie, a positive ATA sample at any time after first IMP administration in a participant with pre-existing ATA but with missing titer at this sample or at baseline).
- Participants **without treatment-emergent ATA** correspond to participants without treatment-induced/boosted ATA and without any inconclusive sample nor unclassified ATA at any time after first IMP administration.
- Participants **with inconclusive ATA** are defined as participants which cannot irrefutably be classified as with or without treatment-emergent ATA.

### ***Kinetics of ATA response***

- Kinetics of ATA response will be derived for participants with treatment-induced/boosted ATA. **Time to onset of ATA response** is defined as the time period between the first IMP administration and the first treatment-induced/boosted ATA.
- **Duration of ATA response** is defined as the time between the first treatment-induced/boosted ATA and the last treatment-induced/boosted ATA, irrespective of negative samples or positive samples not reaching the boosted threshold in-between. ATA duration will be summarized only for participants with persistent ATA response.
  - **Persistent ATA response** is defined by treatment-induced/boosted ATA with a duration of ATA response of at least 16 weeks.
  - **Transient ATA response** is defined by treatment-induced/boosted ATA with a duration of ATA response of less than 16 weeks, and the last sample is not treatment-induced/boosted.
  - **Indeterminate ATA** is defined by treatment-induced/boosted ATA that are neither persistent nor transient.

### ***ATA response variable:***

- **ATA incidence** is defined as the proportion of participants found to have seroconverted (treatment-induced ATAs) or boosted their pre-existing ATA response (treatment-boosted ATAs) at any time after first IMP administration.

#### **4.8.3 Biomarker analyses**

Several exploratory objectives related to pharmacodynamic endpoints will be considered in this study.

Biomarker data will be collected, if available, at prescreening including PD-L1 status by immunohistochemistry (IHC), type of sample (fresh or archived tumor biopsy), tumor mutation/gene alteration status (eg, EGFR, ALK, ROS, MET, RET, BRAF) and circulating CEA.

CEACAM 5 IHC is assessed at prescreening for eligibility of participant for screening to determine if the participant is positive according to the protocol definition: membrane staining at  $\geq 2+$  intensity of  $\geq 50\%$  of tumor cells. In case of re-assessment of CEACAM5 IHC, the most recent tumor tissue samples assessed for CEACAM5 expression will be used for baseline characteristics. All these parameters including type of sample (fresh or archived tumor biopsy) will be described.

##### **4.8.3.1 CEACAM5 by IHC**

In the pre-screened population, the CEACAM5 expression (prevalence of the three categories [negative, moderate and high expressers] and possibly H-score) will be presented using descriptive statistics.

#### **4.8.3.2 Circulating CEA**

The circulating CEA will be considered as a quantitative variable or as a binary variable when considering different binary thresholds: <3, <5, <50, <80 or <100 µg/L.

Circulating CEA values below the LLOQ will be replaced by half of the LLOQ.

##### *4.8.3.2.1 Circulating CEA levels before IMP and CEACAM5 IHC*

Biomarkers analyses described in this section will be performed on participants with available data from the pre-screening population.

Circulating CEA levels before IMP will be correlated with IHC CEACAM5 expression status (for prescreened participants). To this end, the closest circulating CEA assessment to biopsy (or the oldest value before IMP if the date of the biopsy is missing) will be considered. The circulating CEA levels (quantitative and by thresholds) will be presented using descriptive statistics, by IHC CEACAM5 expression status. The correlation between the circulating CEA levels (quantitative) and the CEACAM5 expression will be also assessed, and visualized graphically. To this end, Pearson correlation, Spearman's rank, or Kendall's tau coefficient will be considered depending on the nature of the data. The time from tumor biopsy collection and circulating CEA assessment (the closest to biopsy) will be also described and investigated in the correlation between circulating CEA levels and IHC CEACAM5 expression.

##### *4.8.3.2.2 Potential biomarker for activity*

Circulating CEA levels at baseline will be correlated with confirmed objective response (for all-treated participants). To this end, the last circulating CEA assessment before (closest to) IMP will be considered and reported as the baseline value.

The confirmed objective response rate and two-sided 95% confidence intervals using the Clopper-Pearson method will be presented for each circulating CEA subgroups (based on the predefined thresholds).

The correlation between the circulating CEA levels (quantitative) and the tumor burden at baseline will be also assessed and visualized graphically.

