	
To assess the safety and tolerability of tusamitamab ravidansine in combination with ramucirumabTo assess the durability of the response to treatment with tusamitamab ravidansine in combination with ramucirumabTo assess anti-tumor activity of tusamitamab ravidansine in combination with ramucirumab on progression free survival (PFS) and disease control rate (DCR)To assess the pharmacokinetic (PK) profiles of tusamitamab ravidansine (SAR408701) and ramucirumab when given in combinationTo assess the immunogenicity of tusamitamab ravidansine (SAR408701) when given in combination with ramucirumab	
Incidence of treatment emergent adverse events (TEAEs) and serious adverse events (SAEs) and laboratory abnormalities according to National Cancer Institute (NCI) Common Terminology Criteria for Adverse Events (CTCAE) V5.0Duration of response (DOR), defined as the time from first documented evidence of CR or PR until progressive disease (PD) determined per RECIST v1.1 or death from any cause, whichever occurs firstProgression-free survival, defined as the time from the first investigational medicinal product (IMP) administration to the date of the first documented disease progression or death due to any cause, whichever comes firstDisease control rate (DCR), defined as the percentage of participants who have achieved confirmed CR, confirmed PR or stable disease as per RECIST v1.1Pharmacokinetic parameters of tusamitamab ravidansine (SAR408701) and ramucirumabIncidence of anti-therapeutic antibodies (ATAs) against tusamitamab ravidansine (SAR408701)

Objectives	Endpoints
Tertiary/Exploratory	

• To explore circulating carcinoembryonic antigen (CEA) as a potential biomarker for activity and to evaluate circulating CEA levels at prescreening	
• Circulating CEA at prescreening, screening, and during the treatment period

Abbreviations: ATA=antitherapeutic antibody; BOR=best overall response; CEA=carcinoembryonic antigen; CR=complete response; DLT=dose-limiting toxicity; DCR=disease control rate; DOR=duration of response; IMP=investigational medicinal product; NCI CTCAE= National Cancer Institute Common Terminology Criteria for Adverse Events; NSQ NSCLC=non-squamous, non small-cell lung cancer; PD=progressive disease; PFS=progression-free survival; PK=pharmacokinetic; PR=partial response; RECIST=Response Evaluation Criteria in Solid Tumors.

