## 2 SAMPLE SIZE DETERMINATION

The safety run-in part aims to establish the RP2D of tusamitamab ravtansine in combination with ramucirumab according to DLTs observed.

Part 2 of this study is designed to obtain preliminary efficacy, safety, and PK data on tusamitamab ravtansine administered in combination with ramucirumab to participants with NSQ NSCLC. As the second part is not intended to explicitly test a hypothesis, calculations of power and Type I error were not considered in the study design.

Assuming a pre-screening failure rate of 80% and a study screening failure rate of 20%, approximately 225 participants will be pre-screened to achieve a total of up to approximately 36 treated participants, including Part 1 (safety run-in) and Part 2 of the study.

Sample size of the safety run-in part:

The actual sample size is expected to vary depending on DLTs observed. It is anticipated that around 6 to 12 DLT-evaluable participants (as defined in Section 3) will be enrolled in the safety run-in part of the study.

Sample size of Part 2:

The initial plan is to treat a total of 30 participants evaluable for activity (ie, having at least one post-baseline evaluable tumor assessment, early clinical progression, or death due to disease progression). The 6 participants treated at the RP2D in the safety run-in part will also be evaluable for this second part of the study.

Estimated ORR and 95% exact CIs by number of responders from a sample size of 30 participants evaluable for activity are summarized in Table 4.

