**Table 4 - Estimated objective response rate depending on number of responders**

Number of Responders (N=30)	Objective Response Rate in % (95% Clopper-Pearson CI)
6	20.00% (7.71% - 38.57%)
8	26.67% (12.28% - 45.89%)
9	30.00% (14.73% - 49.40%)
11	36.67% (19.93% - 56.14%)
12	40.00% (22.66% - 59.40%)

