#### 4.3.4 Supplementary analyses

Number (%) of participants within each BOR category, including not evaluable as per RECIST 1.1 and reason for being not evaluable, will be provided on the subgroup of participants from the all-treated population treated at the RP2D (ie, excluding participants treated at the starting dose, if this differs from the RP2D).

As a supplementary analysis, confirmed objective response as per RECIST 1.1 will also be summarized on the subgroup of participants from the activity population (defined in Section 3) treated at the RP2D (ie, excluding participants treated at the starting dose if this differs from the RP2D). The same analytical approach as primary efficacy analysis defined in Section 4.3.2.2 will be used.

In addition, the best relative tumor change from baseline, defined as the smallest relative tumor change from baseline (where tumor change at time t is the difference between sum of the longest diameters of the target lesions at time t and baseline), will be summarized using a waterfall plot on the subgroup of participants from the all-treated population (defined in Section 3) treated at the RP2D (ie, excluding participants treated at the starting dose, if this differs from the RP2D).

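### Baseline CEA is to be correlated with confirmed response, but no scale or method is named and the only specified outputs cut CEA in two

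*SAP*

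**What the plan says.** Protocol section 3 (Table 3) sets the tertiary objective: "To explore circulating carcinoembryonic antigen (CEA) as a potential biomarker for activity and to evaluate circulating CEA levels at prescreening". Protocol 9.4.1 (Table 16) leaves the analysis of circulating CEA to the SAP.

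SAP 4.8.3.2 leaves the scale open: "The circulating CEA will be considered as a quantitative variable or as a binary variable when considering different binary thresholds". The thresholds listed are 3, 5, 50, 80 and 100 µg/L.

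SAP 4.8.3.2.2 deals with activity. It first says that baseline CEA will be correlated with confirmed response in all treated participants, without naming a coefficient, model, plot or scale. The output it specifies is: "The confirmed objective response rate and two-sided 95% confidence intervals using the Clopper-Pearson method will be presented for each circulating CEA subgroups". The word quantitative appears in that section only for a different pairing: "The correlation between the circulating CEA levels (quantitative) and the tumor burden at baseline will be also assessed".

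Three neighbouring sections bear on the point:
- SAP 4.8.3.2.1 names Pearson, Spearman or Kendall coefficients, but for CEA against CEACAM5 expression.
- SAP 4.3.5 includes baseline CEA, split at 100 µg/L, among the response-rate subgroups.
- SAP 4.8.3.2.3 plots change in CEA over time, annotated with best overall response; it does not analyse baseline CEA.

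SAP 4.3.4 derives a continuous measure of activity ("In addition, the best relative tumor change from baseline, defined as the smallest relative tumor change from baseline"), which is used for a waterfall plot and not related to CEA.

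**The concern.** The objective asks whether CEA tracks activity. CEA is continuous, yet every fully specified analysis of its baseline value against response reduces it to two groups, and the outcome is binary as well. A programmer working from SAP 4.8.3.2.2 would produce response-rate tables by threshold. Any quantitative analysis would have to be designed later, possibly after the data had been seen.

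Two things are at stake. The first is precision: each cut spends information that a small trial can ill afford. The second is interpretation. Five nested cuts give 5 × 2 = 10 overlapping response rates from the same participants, and the SAP does not say that the most extreme split must not be singled out.

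**Working it through.** **Inputs from the documents.** For the sample size, SAP section 2 says: "The initial plan is to treat a total of 30 participants evaluable for activity". SAP Table 4 considers 6 to 12 responders out of 30, that is, response rates of 20% to 40%. The cuts come from SAP 4.8.3.2.

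**Assumptions, because the documents are silent.** Log CEA is normal. The odds ratio (OR) for response is 1.5 to 4 per SD of log CEA. The share of participants below a cut is varied from 10% to 80%.

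**1. The plan's own intervals.** Clopper-Pearson limits for x responders in n are the 0.025 quantile of Beta(x, n−x+1) and the 0.975 quantile of Beta(x+1, n−x). For 8 of 30 this gives 12.28% to 45.89%, as in SAP Table 4. The other four rows also reproduce to two decimals.

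**2. The same formula inside CEA subgroups.** Take 9 responders of 30 (overall interval 14.73% to 49.40%):

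| Split | Below the cut | Above the cut |
|---|---|---|
| 15/15 | 4/15: 7.79% to 55.10% | 5/15: 11.82% to 61.62% |
| 6/24 | 1/6: 0.42% to 64.12% | 8/24: 15.63% to 55.32% |

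**3. Information kept by one cut.** For a normal marker cut at quantile p, the share kept is φ(z_p)² / [p(1−p)].

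| Share below the cut | Calculation | Kept | Lost |
|---|---|---|---|
| 50% | 0.3989² / 0.25 | 64% | 36% |
| 30% | 0.3477² / 0.21 | 58% | 42% |
| 20% | 0.2800² / 0.16 | 49% | 51% |
| 10% | 0.1755² / 0.09 | 34% | 66% |

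By symmetry, the same losses apply at 70%, 80% and 90%.

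**4. What this means at N = 30.** Response was simulated from a logistic model in log CEA (4,000 runs per scenario, two-sided 5%, simulation error about 1 point or less). Power serves here only as a yardstick for precision. Each cell gives continuous CEA against a median cut.

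| Response rate | OR per SD | Wilcoxon vs Fisher | Score test vs chi-square |
|---|---|---|---|
| 30% | 1.5 | 15% vs 8% | 16% vs 12% |
| 30% | 2 | 32% vs 17% | 34% vs 23% |
| 30% | 3 | 61% vs 37% | 64% vs 46% |
| 30% | 4 | 77% vs 51% | 79% vs 60% |
| 20% | 2 | 25% vs 13% | 28% vs 18% |
| 40% | 2 | 36% vs 19% | 38% vs 26% |

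The position of the cut matters. With 10% of participants below it, Fisher's test has about 3% power or less for every OR from 1.5 to 4. At a 20% response rate with a cut high in the distribution, the loss can vanish. In a separate run at OR 2 with a 75th-percentile cut, the rank test and the chi-square test both had 25%.

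**The case against.** The strongest reply is that this is a descriptive analysis of an exploratory objective. SAP 4.1 says that the study tests no hypothesis, and no test on CEA is planned, so power comparisons concern tests that nobody will run. The cuts are fixed in advance, all are to be shown, and the SAP proposes no choice among them. These points stand. They limit the severity and make the risk of over-reading a possibility, not a planned defect.

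A reader might also infer three stronger claims, which the documents do not support.

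- **That the threshold table is the only analysis stated.** SAP 4.8.3.2.2 opens with an unspecified correlation, SAP 4.8.3.2 permits quantitative use, and SAP 4.3.5 adds a subgroup analysis. The threshold outputs are the only ones specified for baseline CEA against response, which is a narrower statement.
- **That most of the information is lost.** A balanced cut loses about a third. Five cuts shown together also hold more than one cut does: counts in six ordered bands can be recovered by subtraction. Under the same normal assumption, the bands keep the sum over bands of [φ(lower) − φ(upper)]² / band share. That is 67% with cuts at the 2nd, 5th, 80th, 85th and 88th percentiles, and 82% to 88% in six other placements tried. However, the SAP plans no summary across bands, so this information would sit in the table unused.
- **That the cuts leave the objective unanswerable.** The main limit is about 30 participants with 6 to 12 responders. Continuous CEA reaches roughly 80% power only at an OR of about 4 per SD.

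Relating CEA to tumor change can look far more powerful: 76% to 77% by Spearman at a latent correlation of 0.5, against 34% to 40% for a median split on response. Most of that gap comes from changing the outcome, because the rank test on binary response in the same model gives 44% to 52%.

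**Conclusion.** The point holds in a limited form. The SAP promises a correlation between baseline CEA and response without saying how it will be done, and specifies only dichotomised outputs. Under an assumed normal log CEA, one cut costs about 36% of the information at the median and about half or more from a 20/80 split outward. Where the five cuts would fall in this population cannot be determined from the documents.

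A quantitative analysis would use the same data better in nearly every scenario examined, but it would not make the trial informative about a modest association: power is about 25% to 36% at an OR of 2 per SD. The gain is precision for an exploratory aim. No primary or secondary conclusion is touched, and the change is optional.

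**What to change.** In SAP 4.8.3.2.2, state that the main exploratory analysis treats baseline CEA as quantitative:

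- Compare baseline CEA between confirmed responders and non-responders by a rank-based AUC (Wilcoxon) with a 95% CI and a dot plot.
- In support, give the Spearman correlation between baseline CEA and the best relative tumor change of SAP 4.3.4, with a 95% CI and a scatter plot.
- Use the RP2D-treated set of the primary response analysis (SAP 4.3.2.2). SAP 4.8.3.2.2 now refers to all treated participants; the two sets differ only if the RP2D is not the starting dose.
- Keep the five-threshold response-rate table as description, and state that no cut-point will be selected from it.

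The cost is one paragraph and two outputs from variables already derived. No new data are needed and no type I error is affected. One drawback should be stated: the Spearman analysis omits participants without a post-baseline target-lesion measurement, whereas the AUC analysis keeps them as non-responders.
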